**Protocol Title:** Potential for Cortisol Suppression with the Use of High Volume Nasal Mometasone Irrigations in Varying Dosages

Principal Investigator: [name]

Address: Rush University Medical Center, Department of Otorhinolaryngology – Head and Neck Surgery, [name]

Protocol Version Date: April 20, 2018

Objective:

To determine incidence of cortisol suppression with the use of high volume nasal Mometasone irrigations in varying dosages.

Study Duration: 1 year

Timeframe of study treatment and participation: 12 – 16 weeks

Inclusion Criteria:

- Age 18+
- Diagnosis of Chronic Rhinosinusitis, with or without nasal polyposis
- History of prior endosopic sinus surgery
  - Must include at least ethmoidectomy with maxillary antrostomy

Exclusion Criteria:

- Exposure to systemic corticosteroids within one month of the date of enrollment in to the study.
- Adrenal insufficiency
- Liver disease
- Use of oral estrogens in women
- Morbid obesity (BMI > 38)
- Concurrent pregnancy
- Use of medications which may alter HPA axis(refer to Drugs that affect HPAA)
- Ciliary dysmotility, cystic fibrosis, sarcoidosis, systemic vasculitis, IgG or IgA deficiency, known pituitary or adrenal disease

Intervention:

- 1. Pre study variables to be collected
  - a. Demographic data including MRN, Name, Age, Sex, BMI
  - b. Laboratory data including AM cortisol level and pregnancy testing.
  - c. Imaging data
  - d. Pertinent medical history related to sinus disease

- e. Concomitant medication H/o (Avoid drug interactions refer to the drug interactions section)
- f. Hx of arenal insufficiency and liver disease
- g. Asthma history
- h. Allergy history
- i. ASA intolerance
- j. Smoking history
- k. Lund-Mackay radiographic score
- I. Modified Lund-Mackay endoscopic score
  - i. Only if able to be used preoperative. May be a strictly postoperative scoring system.
- m. Presence/absence of polyps
- 2. Enrolled pts will be randomized on first come first serve into one of the three Mometasone irrigation groups (15 subjects in each dose study group)
  - a. 1mg, 2mg, 4mg BID nasal sinus irrigation dose (see pharmacokinetic calculations in rationale)
- 3. Patients will be followed and treated as standard care. No additional patient visits will be required as part of the research protocol.
- AM cortisol testing will be performed at 12 16 weeks after 12 weeks of continuous topical irrigation use
  - a. Testing will be performed between 6-10 am
    - i. This is the standard in the literature
    - ii. RUMC lab hours 7am-5:30pm M-F
  - b. If patient requires steroid burst for medical reasons, testing schedule will be delayed 1 month from oral steroid use
- 5. Subjects with abnormal blood cortisol levels after 12 weeks of continuous topical irrigation will have a repeat blood cortisol level tested and if abnormal will be follow up with an Endocrinologist.

Drugs which affect the HPAA:

- Mifepristone
- Cyproheptadine, ketanserin, ritanserin, metergoline
- Bromocriptine, cabergoline
- Reserpine
- Valproic acid
- Octreotide, lanreotide, pasireotide
- Pioglitazone, rosiglitazone
- Metyrapone, Trilostane, mitotane, aminoglutethimide, ketoconazole, fluconazole, etomidate
- Sertraline, citalopram, Trazodone
- Clonidine
- MDMA, cocaine, amphetamine
- Methadone, buprenorphine, naltrexone

- Olanzapine, quetiapine, imipramine, desimipramine, clomipramine, mirtazapine
- Medroxyprogresterone, megestrol, Raloxifene
  Drug Interactions
- Avoid combination with Desmopressin
- Monitor therapy while on
  - A. CYP3A4 Inhibitors (Strong) Interacting Members Atazanavir; Boceprevir; Clarithromycin; Cobicistat; Darunavir; Idelalisib; Indinavir; Itraconazole; Ketoconazole (Systemic); Lopinavir; MiFEPRIStone; Nefazodone; Nelfinavir; Ombitasvir, Paritaprevir, and Ritonavir; Ombitasvir, Paritaprevir, Ritonavir, and Dasabuvir; Posaconazole; Ritonavir; Saquinavir; Telaprevir; Telithromycin; Voriconazole
  - B. Ceritinib.
  - C. Ritodrine

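### Strong CYP3A4 inhibitors, ceritinib and ritodrine are allowed under an undefined monitoring instruction: only 2 of the 21 listed inhibitors are excluded, and no on-treatment cortisol is planned before 12-16 weeks

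*Protocol*

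**What the plan says.** Four parts of the protocol bear on co-medication.

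- **Exclusion Criteria.** The medication criterion reads "Use of medications which may alter HPA axis(refer to Drugs that affect HPAA". It names no drug itself; its content is the list headed Drugs which affect the HPAA. That list includes mifepristone and the line "Metyrapone, Trilostane, mitotane, aminoglutethimide, ketoconazole, fluconazole, etomidate".
- **Intervention, item 1e.** Under "Pre study variables to be collected", staff take a concomitant medication history with the note "Avoid drug interactions refer to the drug interactions section".
- **Drug Interactions.** The section has two grades. The first is "Avoid combination with Desmopressin". The second, "Monitor therapy while on", covers three items: strong CYP3A4 inhibitors (the list opening "CYP3A4 Inhibitors (Strong) Interacting Members Atazanavir; Boceprevir; Clarithromycin; Cobicistat; Darunavir; Idelalisib; Indinavir; Itraconazole"), ceritinib and ritodrine.
- **Intervention, items 3 to 5.** "Patients will be followed and treated as standard care", with no research visits added. Morning cortisol is measured before the study and again at 12-16 weeks. Item 4b postpones testing by a month after an oral steroid burst. Item 5 calls for a repeat cortisol after an abnormal result and, if that is also abnormal, an endocrinologist.

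The SAP specifies a paired t-test on pre- and post-treatment cortisol. It does not mention co-medication.

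**The concern.** The objective is the incidence of cortisol suppression at three mometasone doses. If a subject also takes a drug that the protocol lists as interacting with the study steroid, an abnormal cortisol cannot be assigned cleanly to the dose. The protocol recognises this kind of problem elsewhere: it excludes drugs acting on the HPA axis and delays testing after oral steroids. For the monitored drugs it gives staff an instruction that they cannot carry out, because nothing says what to measure, when, or what to do with the result.

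Two things are at stake. One is attribution of suppression to dose in arms of 15. The other is the safety of a subject who irrigates for at least 12 weeks on a listed interacting drug, under a monitoring instruction with no content. Two drugs also carry incompatible instructions.

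**Working it through.** **1. Compare the two lists.** The inputs are the strong-inhibitor entries under Drug Interactions, split at semicolons, and the drugs under Drugs which affect the HPAA.

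- Strong CYP3A4 inhibitor entries: 21.
- Of these, also on the HPAA list: 2 (ketoconazole, mifepristone).
- Not on the HPAA list: 21 − 2 = 19, and 19/21 = 90%. This is a share of drug names, not of patients.
- Ceritinib and ritodrine: neither is on the HPAA list.

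**2. Read off the rule for each group.**

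| Group | Exclusion criterion (via HPAA list) | Drug Interactions |
|---|---|---|
| Ketoconazole, mifepristone | excluded | monitor |
| Other 19 inhibitor entries | not excluded | monitor |
| Ceritinib, ritodrine | not excluded | monitor |
| Desmopressin | not excluded | avoid |

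Only the first row contains a direct contradiction. Rows two and three are consistent: enrolment is allowed, with monitoring.

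**3. Look for the content of the monitoring.** Planned cortisol measurements are baseline (item 1b), 12-16 weeks (item 4), and a repeat only if that result is abnormal (item 5). On-treatment cortisols before week 12: 0. Item 4b can only move the test later. Item 1e is a pre-study variable, and no later medication check is stated, so a drug started during irrigation need not be recorded.

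**4. Effect on incidence.** There are 15 subjects in each of three dose groups, 45 in all. One case to which a listed drug contributed is:

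- arms reported separately: 1/15 = 6.7 percentage points;
- arms pooled: 1/45 = 2.2 percentage points.

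The SAP does not say which applies. Any single misattributed subject would count the same, so these figures are the weight of one case and not an estimate of bias.

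**5. Effect on the paired t-test.** Assume that one subject in an arm of 15 has a cortisol change shifted by k standard deviations, with no other effect present. The mean change moves by k/15, and the expected t is approximately (k/√15)/√(1 + k²/15).

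| k (assumed) | Shift in mean (SD) | Approximate t |
|---|---|---|
| 1 | 0.07 | 0.25 |
| 2 | 0.13 | 0.46 |
| 3 | 0.20 | 0.61 |

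The two-sided 5% critical value on 14 degrees of freedom is 2.14, and the SAP plans for an effect of 1.0 SD. One such subject would not drive the test.

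The SAP's sample size of 13 reproduces with a one-sided paired t-test at d = 1.0 and alpha 0.05 (power 0.960 at 13, 0.945 at 12), and also with a two-sided normal approximation. Nothing in this point depends on it.

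**The case against.** **Item 1e does not contradict the section it cites.** A reader might infer that item 1e says avoid while the Drug Interactions section says monitor, so that all 21 entries are neither clearly excluded nor clearly permitted. The documents do not support that. Item 1e is a pointer, and the section it points to grades the response: avoid one drug, monitor the rest. An instruction to monitor presupposes co-use. The 19 entries are therefore permitted, and the true conflict is limited to the two double-listed drugs. This part of the objection stands.

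**The causal link is not in the documents.** They give no mechanism, direction or size for the interaction. The Mometasone Study Rationale relies on 99% first-pass removal of swallowed mometasone, and liver disease is an exclusion, so hepatic clearance matters to the protocol's own safety case. But the protocol never names CYP3A4 as the route. It says only that these drugs interact and call for monitoring. That is enough to require a rule, but not enough to predict the harm.

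**There is a safeguard.** Item 5 gives a subject with an abnormal result a repeat test and, if needed, an endocrinologist. This has real value for the individual. It acts only after an abnormal result at 12 weeks or later, however, and it does not separate dose from co-medication.

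**The early gap in testing is general.** No subject has an on-treatment cortisol before week 12. That is the design, and not in itself a fault of the interaction rule. It matters here because the interaction rule promises monitoring and the schedule supplies none.

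**Defining the monitoring would be a smaller change.** It would, and it would address the safety gap. But an early cortisol would add a blood test, and the co-medication would still be present when the endpoint is measured.

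**Conclusion.** The point holds in a limited form. The protocol permits 19 of the 21 listed strong CYP3A4 inhibitors, plus ceritinib and ritodrine, under a monitoring instruction with no action attached. It gives ketoconazole and mifepristone two incompatible instructions. It has no way of recording a listed drug started during irrigation, and the SAP has no rule for such subjects.

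The consequence is an avoidable confounder of the incidence by dose and a modest individual safety risk. A reader might infer that the trial's main comparison is compromised, or that 6.7 points is an expected bias. Neither follows. The t-test shift is at most 0.20 SD for one subject under the assumed 1 to 3 SD, and the number of exposed subjects is unknown and could be zero. The change should be made because it is cheap and extends an exclusion that the plan already uses. Confidence is medium, because the size of the interaction and the frequency of use are not in the documents.

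**What to change.** 1. Add the protocol's own monitor list (the strong CYP3A4 inhibitors, ceritinib and ritodrine) to the exclusion criteria at enrolment, and delete the monitoring instruction. This also removes the double listing of ketoconazole and mifepristone.
2. Do not prohibit clinically needed treatment during the study, which would sit badly with item 3. Instead, ask about concomitant medication at the existing 12-16 week draw, and record the drug and dates for any listed drug started during irrigation.
3. State in the SAP that cortisol results will be reported with and without those subjects.

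The cost is slightly narrower eligibility and one added question. No visit, blood test, dose, arm or planned test changes. One limit remains: a question at the final draw finds a mid-study start afterwards and does not prevent it, so item 5 is still the only safeguard for that subject.

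The SAP is dated 8/10/2021 and written in the past tense. If enrolment is already complete, the reporting step still applies: the item 1e histories can identify baseline users, and any mid-study medication records can be checked.

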## Mometasone Study Rationale

The addition of budesonide 0.5 mg/2 ml respules to nasal irrigations has become common practice in the treatment of chronic rhinosinusitis. The dose of budesonide 0.5 mg/2 ml was chosen as a result of convenience, as budesonide respules are commercially available as an inhalation in the treatment of asthma. Mometasone is an alternative to budesonide with improved pharmacokinetics resulting in increased local efficacy and lower systemic absorption, however, data is limited in its use as a topical irrigation formulation.

There is relevant literature available discussing the pharmacokinetic profile of budesonide and mometasone used intranasally. Following intranasal administration a drug may enter systemic circulation through direct local absorption in the nasal mucosa or oral absorption of any swallowed medication. The intranasal bioavailability of budesonide and mometasone through nasal mucosa have been measured at 34% and <0.1% respectively. If a drug enters systemic circulation through the nasal mucosa, the medication is subject to plasma protein binding. When a medication is protein bound it is not bioactive and thus reduces the potential for systemic adverse effects. Approximately 85-90% of budesonide is bound to plasma proteins after entering systemic circulation. Alternatively, mometasone is 99% protein bound at clinically relevant concentrations. Therefore, budesonide is bioactive at 10-15 times the concentration of mometasone in the serum due to plasma protein binding.

A portion of the drug may also be cleared from the sinuses into the throat and swallowed, making it available for gastrointestinal absorption. Medications absorbed through the gastrointestinal tract are subject to first pass hepatic metabolism which largely determines the amount of medication which reaches systemic circulation. Approximately 90% of swallowed budesonide is metabolized by the liver during first pass metabolism^7. On the other hand, when mometasone is swallowed and undergoes first pass metabolism, 99% of the drug is eliminated leaving only 1% of the drug to enter the circulation.

A desired pharmacokinetic property of intranasal steroids is high lipophilicity. Higher lipophilicity leads to increased intranasal absorption as well as prolonged retention in the nasal tissue. Longer retention of the steroid in nasal tissue results in increased exposure to the glucocorticoid receptor. The relative lipophilicity of budesonide and mometasone are 3,980 and 50,000 respectively. Thus, mometasone has twelve times higher lipophilicity than budesonide.

In order to determine the proper dose of mometasone, it is important to take into account the volume of nasal irrigation that will remain in the sinus cavity. In patients who have undergone endoscopic sinus surgery, after performing a nasal irrigation with a 240 ml saline filled Neilmed bottle, the result is 1.2% to 5% of the solution remaining in the sinuses. Therefore, the maximum amount of fluid left in the sinuses after a 240 ml nasal irrigation is 5% of the total volume or 12 ml. Applying this data one may estimate the maximum absorption of mometasone added to a 240 ml saline filled Neilmed bottle for irrigation.

• Mometasone 1 mg capsule dissolved in 240 mg

0

- 1 mg/ 240 ml = 0.00416 mg/ml or 4.16 mcg/ml
  - Max volume that can be retained in sinuses is 12 ml
  - 12 ml x 4.16 mcg/ml = 50 mcg
  - Medication dosed twice daily, therefore total daily dose = 100 mcg
- Mometasone 2 mg capsule dissolved in 240 mg
  - 2 mg/ 240 ml = 0.00833 mg/ml or 8.33 mcg/ml
    - Max volume that can be retained in sinuses is 12 ml
    - 12 ml x 8.33 mcg/ml = 100 mcg
    - Medication dosed twice daily, therefore total daily dose = 200 mcg
- Mometasone 4 mg capsule dissolved in 240 mg
  - 4 mg/ 240 ml = 0.0166 mg/ml or 16.6 mcg/ml
    - Max volume that can be retained in sinuses is 12 ml
    - 12 ml x 16.6 mcg/ml = 200 mcg
    - Medication dosed twice daily, therefore total daily dose = 400 mcg

Mometasone nasal spray is currently FDA approved at a dose of 2 sprays (100 mcg) in each nostril twice daily for the treatment of nasal polyps. Total daily dose is 400 mcg++. Therefore even at a dose of mometasone 4 mg used in a 240 ml nasal irrigation, the total daily dose is equivalent to that of the mometasone nasal spray.

There is current relevant data to assess the safety of mometasone administered intranasally. A review of 20 clinical trials with more than 6,000 patients worldwide at doses up to 20 times the recommended daily dose found no detectable effect of mometasone on the hypothalamic-pituitary-adrenal axis (HPA). Additionally, mometasone at high doses, did not cause atrophy to the nasal mucosa. Intranasal mometasone at a dose of 1600 mcg, which is 4 times the recommended dose administered daily to human volunteers for 29 days showed no incidence of adverse

effects. The effects of oral mometasone on HPA axis function has also been studied. Oral mometasone was administered at doses of 2, 4, and 8 mg to 24 healthy male volunteers with no significant change in plasma or urinary cortisol from placebo.

Drug remaining after first pass metabolism	10%	1%
Plasma protein binding	85-90%	99%
Relative lipophilicity	3980	50,000

## Potential for Cortisol Suppression With the Use of High Volume Nasal Mometasone Irrigations in Varying Dosages.

NCT03979209

8/10/2021

Statistical Analysis Plan

An a priori analysis using G\*3.0.10 Power was performed in order to determine adequate sample size. Using a Cohen's D of 1.0, alpha of 0.05 and power of 0.95, sample size was determined to be 13. Pre- and post-treatment morning cortisol serum levels were compared using a match paired, dependent sample Student's *t*test. Significance was established at *P*<0.05. All data acquired during this study were de-identified to protect patient privacy, and identifying information was only available to the principal investigator.

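### Must the SAP be changed because it does not say whether the 13 patients and the paired t-test are per dose group or pooled over the three doses?

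*SAP*

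**What the plan says.** The SAP is a single paragraph. The effect size is given by "Using a Cohen's D of 1.0", and the same sentence ends "alpha of 0.05 and power of 0.95, sample size was determined to be 13". The analysis sentence reads "Pre- and post-treatment morning cortisol serum levels were compared using a match paired, dependent sample Student's" t-test, with significance at P<0.05. Outside its title, the SAP does not mention dose. It does not give the number of tails, and it does not say whether d is scaled by the SD of the paired change or by the SD of a single cortisol value.

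The protocol's Objective is "To determine incidence of cortisol suppression with the use of high volume nasal Mometasone irrigations in varying dosages". Item 2 under Intervention assigns patients to "one of the three Mometasone irrigation groups (15 subjects in each dose study group"), which makes 3 × 15 = 45 patients. The protocol has no power calculation and does not link its 15 to the SAP's 13.

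**The concern.** The trial varies the dose in order to learn whether cortisol falls at any of the doses, so the unit of analysis matters. If the t-test is run once over all patients, a fall confined to one dose is diluted by the other two groups. A non-significant pooled P-value could then be read as no suppression at any dose, and the stated 95% power would seem to support that reading. In a safety question, false reassurance is the costly error.

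The unstated tails add to the doubt. An exact two-sided paired test with d = 1.0 on the SD of the change needs 16 patients, not 13, so at first sight the sample size itself looks wrong.

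**Working it through.** **Inputs.** From the SAP: d = 1.0, alpha 0.05, power 0.95, n = 13, paired t-test. From the protocol: three groups of 15, at 1, 2 and 4 mg twice daily. Assumed, because not stated: d is mean change divided by SD of change, except where noted. The patterns of change across doses in step 3 are also assumptions.

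**1. Reproducing the 13.** For a paired t-test, power = P(T > t_crit), where T is noncentral t with n − 1 degrees of freedom and noncentrality d√n. The two-sided version adds the lower tail, which is negligible here.

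- n = 12: noncentrality √12 = 3.464; power 0.883 two-sided, 0.945 one-sided.
- n = 13: noncentrality √13 = 3.606; power 0.911 two-sided, 0.960 one-sided.
- n = 16: power 0.962 two-sided.

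The smallest n reaching 0.95 is 13 one-sided and 16 two-sided. The SAP's 13 therefore reproduces exactly with a one-sided test. One-sided is an inference: a two-sided normal approximation gives (1.960 + 1.645)² = 12.99, which also rounds up to 13.

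**2. One test per dose group, at the planned 15.** Noncentrality √15 = 3.873; power 0.949 two-sided, 0.979 one-sided. With 15 patients analysed per group, the choice of tails moves power by 0.979 − 0.949 = 0.030, and both values are close to or above the intended 0.95.

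**3. One pooled test on 45.** Take SD of change = 1 within each dose. Pooling gives mean change m and SD of about √(1 + v), where v is the variance of the three dose means. For changes of 0, 0 and 1.0 SD:

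- m = 1/3 = 0.333 and v = 2/9
- effective d = 0.333/√(1 + 0.222) = 0.302
- noncentral-t two-sided power at 45 = 0.507

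Simulation of the pooled test under four patterns gives:

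| Assumed change by dose (SD) | Two-sided power | One-sided power |
|---|---|---|
| 0, 0, 1.0 | 0.51 | 0.65 |
| 0, 0.5, 1.0 | 0.88 | 0.94 |
| 0.25, 0.5, 1.0 (proportional to dose) | 0.96 | 0.98 |
| 1.0, 1.0, 1.0 | >0.999 | >0.999 |

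The pooled test is much weaker than the 0.949 within one group in the first row and somewhat weaker in the second. It is at least as strong in the third and fourth.

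**4. Multiplicity, if three tests are run.** Three independent tests at 0.05 give 1 − 0.95³ = 0.143 for at least one false positive. At 0.05/3 = 0.0167 each, two-sided power at 15 is 0.858.

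**The case for a change.** The strongest case for acting is that neither document resolves the unit, that the remedy would be two or three sentences, and that the answer decides what the only stated test can show about dose. Even if 13 is per dose, the t-test itself could still be pooled. If it is run three times at P<0.05, no adjustment is mentioned.

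The silence stands, and so does the 0.51 for an effect confined to one dose. The weight placed on them does not. The harm needs four things together: a pooled-only analysis, an effect in one dose alone, a non-significant result, and a reading of that result as safety at every dose. The documents establish none of them. A total of 13 patients, 4 or 5 per dose, matches nothing in a protocol that plans 45, whereas 13 sits naturally beside 15 per group with a small margin. The value of d is stated; only its scaling is not. On multiplicity, the three tests concern a safety signal, so leaving them unadjusted favours detection. The price is the 14.3% false-positive chance, which a reader can see and allow for.

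**Conclusion.** No change follows. The SAP leaves out the unit of analysis, the tails and the scaling of d, but its 13 is correct for a one-sided paired t-test. The reading that agrees with the protocol's design, one pre/post comparison in each dose group, has power 0.949 two-sided or 0.979 one-sided at 15. An analyst working from a protocol with three dose groups and an objective framed by dose would be expected to report the change in each group, and the cortisol values for that are already collected.

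The conclusion rests on d being mean change over SD of change, on about 15 patients per dose contributing paired values, and on the per-dose reading. That reading is the best fit to the documents but is not stated in them. If only a pooled test on 45 were reported, a non-significant result could not by itself exclude a 1.0 SD fall at a single dose, since two-sided power for that pattern is about 0.51.

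### The objective is the incidence of cortisol suppression, but the only planned analysis is a paired t-test on mean cortisol, which estimates no incidence and can miss a suppressed minority

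*SAP*

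**What the plan says.** The Objective in the protocol reads: "To determine incidence of cortisol suppression with the use of high volume nasal Mometasone irrigations in varying dosages". No other objective is given. Patients are allocated to three irrigation doses, with "15 subjects in each dose study group", so 45 in all. Morning cortisol is measured before treatment (Intervention, item 1b) and again after 12 weeks of irrigation.

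Intervention item 5 already sorts patients one by one: "Subjects with abnormal blood cortisol levels after 12 weeks of continuous topical irrigation will have a repeat blood cortisol level tested". A second abnormal result leads to specialist follow-up. The protocol gives no cut-off for abnormal and does not use the classification as an outcome.

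The SAP is a single paragraph. Its sample size is for a mean effect: "Using a Cohen's D of 1.0, alpha of 0.05 and power of 0.95, sample size was determined to be 13". Its only analysis is also of a mean: "Pre- and post-treatment morning cortisol serum levels were compared using a match paired, dependent sample" t-test. The decision rule is "Significance was established at *P*<0.05", with no statement of one or two sides. Neither document plans a count or proportion of suppressed patients, or a confidence interval for one, by dose or overall.

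**The concern.** Incidence and mean change are different quantities. Incidence asks how many patients become suppressed. The t-test asks whether the average cortisol moved. If a few patients are strongly suppressed and the rest are not, the mean moves little, and those same patients widen the SD of the changes, which shrinks the t statistic further.

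This is a safety question, so the direction of the error matters. The SAP has no rule for reading a non-significant result, and a reader could easily take P>0.05 as showing no suppression. With 15 patients per dose that would be false reassurance. The result that would answer the question, each patient's status as abnormal or not, is obtained for clinical follow-up and then left out of the analysis.

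**Working it through.** **1. The plan's own figure.** Inputs from the SAP: d = 1.0, alpha 0.05, power 0.95. Power of a paired t-test comes from the noncentral t distribution with n − 1 degrees of freedom and noncentrality d√n.

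- One-sided: n = 12 gives 0.945 and n = 13 gives 0.960, so N = 13 reproduces.
- Two-sided, exact: n = 13 gives 0.911, and 16 are needed (0.962).
- Two-sided, normal approximation: (1.960 + 1.645)² = 12.99, so 13.

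The stated 13 is therefore a sample size for detecting a shift in the mean of one SD. It says nothing about the precision of an incidence estimate.

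**2. What the planned numbers can say about incidence.** Exact (Clopper-Pearson) 95% limits. With no cases the upper limit is 1 − 0.025^(1/n).

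| Suppressed / n | 95% interval |
|---|---|
| 0/15 | 0 to 21.8% |
| 1/15 | 0.2 to 31.9% |
| 2/15 | 1.7 to 40.5% |
| 0/45 | 0 to 7.9% |

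If the true incidence were 10%, a group of 15 would show no case with probability 0.9¹⁵ = 20.6%. For 45 it is 0.9⁴⁵ = 0.9%. None of this depends on a cortisol SD or an effect size.

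**3. What the t-test would detect.** The documents give no SD of change, size of fall or expected incidence, so these are assumptions: change normally distributed with SD 3, 4 or 5 mcg/dL, suppressed patients falling by 8 or 10 mcg/dL, the others unchanged on average.

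One case by hand, with 3 of 15 suppressed, a fall of 9 and SD 4:

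- Mean fall = 3 × 9 / 15 = 1.8 mcg/dL.
- Expected variance of the changes = 4² + 9² × 3 × 12 / (15 × 14) = 16 + 13.9 = 29.9, so the SD rises from 4 to 5.47.
- t ≈ 1.8 / (5.47 / √15) = 1.28, against a two-sided critical value of 2.145.

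Simulated chance of a significant fall, as the range over the assumed SDs and falls:

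| Suppressed / n | Two-sided 0.05 | One-sided 0.05 |
|---|---|---|
| 2/15 (13%) | 7 to 9% | 14 to 19% |
| 3/15 (20%) | 12 to 18% | 22 to 36% |
| 6/45 (13%), pooled | 20 to 47% | 32 to 67% |
| 9/45 (20%), pooled | 41 to 85% | 56 to 94% |

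A second set-up gives the same picture. Each patient has a 10% or 20% chance of suppression, with a fall of 2 to 3 SDs of the change. At n = 15 the two-sided detection rate is 7.6 to 8.6% at 10% incidence and 17.7 to 23.7% at 20%.

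**4. Precision of the mean itself.** The 95% half-width at n = 15 is 2.145 / √15 = 0.55 SD of the change.

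**The case against.** Five points can be made for the plan.

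- *A count is still possible.* Item 5 has every post-treatment result judged abnormal or not, and the SAP does not forbid tabulating it. That is so. But a table that could be made is not a planned analysis. With no cut-off, denominator or interval fixed, the result would depend on choices made later.
- *The SAP never says that P>0.05 means no suppression.* Correct. The misreading is a risk, not a statement in the text. The SAP offers nothing else from which to draw a conclusion.
- *The simulation models the pattern least favourable to a mean test.* Also fair. If every patient fell by 3 mcg/dL, two-sided power at n = 15 would be 95%, 77% and 58% for SDs of 3, 4 and 5, and at least 97.5% at n = 45. Pooling at 20% incidence also does much better than a single dose group. The simulation shows that the test can miss a minority, not that it always would, and no more than that is claimed.
- *Any cut-off is a choice that the documents do not make, and one fixed limit may act differently across the draw window* ("Testing will be performed between 6-10 am"). This stands as a reason for the sponsor to state and justify the definition. It is not a reason to have none.
- *The SAP is dated 2021 and written in the past tense, so a new primary outcome may be post hoc.* This stands and belongs in the fix.

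**Conclusion.** The concern holds. The trial's only objective is a proportion, and its only analysis is a test of a mean. This can be read directly from the two documents and needs no assumption. The exact limits (0/15 allows up to 21.8%, 0/45 up to 7.9%) rest only on the planned group sizes. The detection rates of 7 to 9% with 2 of 15 suppressed and 12 to 18% with 3 of 15 (two-sided) rest on the assumed SD, the assumed fall and the assumption that the other patients do not change, so they are illustrative. This must be fixed, because as written the plan prespecifies no answer to its own question and a non-significant result could be mistaken for evidence of safety.

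**What to change.** In the SAP:

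1. Define suppression for the analysis and justify the definition. A morning cortisol below the laboratory's lower reference limit at 12 to 16 weeks is a natural candidate, because that limit is set outside the trial and fits the protocol's notion of an abnormal level. State how draw time within the morning window is handled.
2. Make the primary outcome the proportion suppressed, by dose group and overall, among patients whose baseline value was in range. Report it on the first post-treatment test and again as confirmed on repeat, each with an exact 95% interval. State when the repeat is taken.
3. Keep the paired comparison as secondary. Use the first post-treatment value, state the sidedness, and report the mean change with its 95% interval.
4. State that P≥0.05 will not be read as absence of suppression.
5. Date the change. If anyone had seen outcome data by then, label the new primary outcome post hoc.

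The cost is SAP text. Baseline, post-treatment and repeat cortisol are already in the protocol, so no visit, test or patient is added, and the clinical handling of abnormal results is untouched. The drawback is that the published intervals will look wide: about 22 percentage points for a dose group with no cases.
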